### **5.8.1.6 Replacing subjects**

Case data for all enrolled study subjects will be included in the analyses. Because a subject's involvement ends following his biopsy procedure, and because it is not expected that a subject will drop-out after his biopsy procedure, the need to replace subjects is expected to be unlikely.

If a subject needs to be replaced, he will be consented as per processes described for all study subjects.

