### **5.8.5.1 Site Visits**

Further to the description of Exact Imaging's role as the Study Monitor for the investigation, Exact Imaging will ensure the quality of data related to the investigation by:

- on-site visits to Urology San Antonio at the beginning and end of the study
- thorough review of CRF data to identify and follow-up on missing data, inconsistent data, data outliers, and potential CIP deviations that may be indicative of systemic or significant errors in data collection and reporting
- 100% verification of all data

An on-site visit at the beginning of the investigation will include the following activities:

1. Review of supplies required for the investigation
  - a. Check that there continues to be an adequate supply of sterile transducer sheaths and needle guides

An on-site visit at the beginning of the investigation will include the following activities:

1. Review issues with investigators
  - a. Study Monitor will discuss and investigate any performance issues and device deficiencies and resolved as required. These issues will be documented and signed by the Study Monitor, including details about steps taken to resolve issues
  - b. Review any changes to the investigative team and update details in the CIP as required
  - c. Provide training where changes to the investigative team requires it
2. Review subject enrolment
3. Review study data
  - a. Review data collected on CRF
  - b. Check CRF for completeness and accuracy. Ensure CRFs are filled out properly
  - c. Check ExactVu for images. There must be one image saved on the system to correspond to each biopsy core.

- d. Verify data. Compare images stored on ultrasound system with CRF data and pathology report
4. Copy and collect image data
5. Copy and collect completed CRFs

Along with providing assurance of the quality of investigational data, these actions will allow Exact Imaging to assess compliance with the CIP and required procedures.

For cases in which the Study Monitor observes biopsy procedures during a site visit, the Study Monitor shall neither perform medical procedures nor contact the study subject, but will provide support through instruction where required.

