### **5.8.6 Case Report Forms**

The case report form to be used in this investigation is designed to collect information about the location of the prostate where biopsy samples were taken, to provide a summary of findings from the pathology report entered locally, along with other notes from investigators.

Source data will be recorded on case report forms (CRFs) as follows:

- For each of the 12 systematic biopsy samples, investigators will indicate the PRI-MUS score for micro-US. (For every biopsy sample, an image of the biopsy location will be saved on ExactVu as well.)
- For each additional targeted biopsy sample, investigator will indicate the location and the PRI-MUS score for micro-US. (For every biopsy sample, an image of the biopsy location will be saved on ExactVu.)
- Pathology report will be entered on the CRF and a copy attached to the CRF. This is checked for accuracy by the Principal Investigator.
- mpMRI report will be entered on the CRF and a copy attached to the CRF. This is checked for accuracy by the Principal Investigator.

Note that the PRI-MUS protocol used here is derived from Ghai et al.. This protocol for assessing risk in the micro-US images is investigational and has not been evaluated by the FDA.

Along with the data accuracy checks listed above, Exact Imaging will also check data prior to and during analysis as follows:

- Check pathology reports against what is entered on the CRF
- Logic checks on data, and follow-up on unusual data. (For example, if there is a case in which biopsy samples from targeted needles don't indicate cancer and samples from systematic needles do show cancer, an investigation would follow.)

Analysis of data is described in the subsections of section 5.9.

The case report form to be used in this investigation is controlled as per Exact Imaging's standard operating procedures.

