### **5.9.8 Specification of subgroups for analysis**

All analyses will be conducted on all enrolled and completed subjects. These analyses will also be repeated on the "As Intended" population, which includes only subjects for which there were no major protocol deviations.

A low risk sub-population is pre-specified for analysis. This population includes men meeting all of the following criteria:

1. PSA < 20ng/ml
2. PSAD < 0.15 ng/ml/cc
3. Negative DRE

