### **5.9.9 Procedures that take into account all data**

Statistical analyses around study endpoints will not include data for subjects who are withdrawn (before or after their biopsy) or for whom the collected study data is incomplete.

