#### **5.9.10 Treatment of missing, unused data**

If a study subject withdraws from the main trial prior to having his biopsy, his consent form will be retained, and the reason for exclusion of the data will be handwritten on the form as "withdrawn prior to biopsy". Similarly, if a study subject withdraws from the main trial following his biopsy, his consent form and CRF will be retained, and both will be marked "withdrawn following biopsy".

This will allow data to be collected about the number of patients that withdrew from the investigation prior to the biopsy procedure, and the number that withdrew after the procedure.

The same process will be applied to any circumstance of incomplete or incorrect data, with an indicator handwritten on his consent form and CRF to provide information about why the record is not used for analysis.

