#### **5.9.11 Exclusion of data**

Conditions that would result in the exclusion of data would be if any data verification activity showed that data was recorded on the CRF incorrectly, or if the pathology report showed any inconsistency with information on the CRF.

If such incorrect data was discovered, data for this subject will not be included in any analysis, and the CRF for the subject will be marked to indicate that the data is excluded.

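### The incomplete-data rule in 5.9.9 excludes whole subjects from every endpoint analysis, does not define incomplete data, and can remove men whose csPCa result is known for both modalities

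*Combined protocol and SAP*

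**What the plan says.** Section 5.9.9 bars two groups from the endpoint analyses: withdrawn subjects, and those "or for whom the collected study data is incomplete". The unit removed is the subject, not the missing item, and the bar covers every endpoint. Section 5.9.10 marks such records as unused and adds: "The same process will be applied to any circumstance of incomplete or incorrect data". Neither section lists required items or sets a threshold. Section 5.9.11 is a separate rule for CRF errors, with the same whole-subject consequence: "data for this subject will not be included in any analysis".

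Two other sections describe the analysed population differently. Section 5.8.1.6: "Case data for all enrolled study subjects will be included in the analyses". Section 5.9.8: "All analyses will be conducted on all enrolled and completed subjects", with no definition of completed.

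Under 5.8.1.3 the primary endpoint is determined from biopsy results, targeted and systematic. The study collects more than that. Section 5.8.6: "For each of the 12 systematic biopsy samples, investigators will indicate the PRI-MUS score for micro-US", and likewise for each targeted sample. Section 5.8.5.1: "There must be one image saved on the system to correspond to each biopsy core". Section 5.8.1.3 also has lesion size and shape recorded.

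**The concern.** A man can have full pathology from both operators and still lack a score for one core or an image of another. His contribution to the paired sensitivity comparison is then fully known. Taken at its word, 5.9.9 discards it for want of an item that the comparison does not use.

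Two things are at stake. The first is information on the primary endpoint, lost for no analytical reason. The second is selection. An undefined exclusion rule leaves someone to decide who is incomplete, and under 5.8.5.1, 5.8.6 and 5.10.2 sponsor personnel compare CRFs and images with the pathology reports. The decision could therefore be taken with outcomes in view. In a non-inferiority comparison of the sponsor's own device, the analysed set should not depend on such a judgement.

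**Working it through.** **1. Is the lost item needed?** Primary endpoint (5.8.1.3): pathology of systematic and targeted cores. PRI-MUS score (5.8.6) and image per core (5.8.5.1, 5.8.6): not needed to know whether a core contained csPCa. So the literal rule can remove men with a known primary result.

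**2. Do the sections agree?** Section 5.8.1.6 takes all enrolled subjects, 5.9.8 takes enrolled and completed subjects, and 5.9.9 takes those neither withdrawn nor incomplete. These are three different populations for the same primary analysis.

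**3. The plan's own sample size.** Inputs: sensitivities 0.85 (micro-US) and 0.90 (mpMRI), agreement 80%, power 80% (5.9.3); prevalence 60% and margin 0.76 (5.9.1); one-sided 5% (5.9.5). Discordance is 0.20, so p10 (micro-US only) = (0.20 − 0.05)/2 = 0.075, p01 (mpMRI only) = 0.125, and p11 (both) = 0.85 − 0.075 = 0.775.

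Paired log-ratio formula: n = (1.645 + 0.842)² × [0.20/(0.85 × 0.90)] / [ln(0.85/0.90) − ln 0.76]² = 6.18 × 0.2614 / 0.2173² = 34.2 csPCa men, so N = 34.2/0.60 = 57.1, or 58. The stated 120 is not reproduced. That is a separate matter; here it means only that 120 carries more than 80% power on these inputs.

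**4. Power as men are lost.** Expected csPCa men: 120 × 0.60 = 72. Power = Φ(0.2173/√(0.2614/n) − 1.645).
- n = 72: Φ(3.606 − 1.645) = 97.5%.
- n = 57: Φ(3.208 − 1.645) = 94%.
- n = 36 (half lost): Φ(2.550 − 1.645) = 82%.

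Simulation gives 95.7% with no loss and 78% with half lost.

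**5. How many might be lost.** The documents give no missingness rate. Assume each item is missing independently with probability q, with k items per man; k = 24 is 12 scores plus 12 images. The complete fraction is (1 − q)^k.

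| q | k | complete | csPCa men left of 72 | power (formula) |
|---|---|---|---|---|
| 0.2% | 24 / 32 | 95% / 94% | 68.6 / 67.5 | 97% / 97% |
| 0.5% | 24 / 32 | 89% / 85% | 63.8 / 61.3 | 96% / 95% |
| 1% | 24 / 32 | 79% / 73% | 56.6 / 52.2 | 94% / 92% |
| 2% | 24 / 32 | 62% / 52% | 44.3 / 37.7 | 88% / 83% |

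**6. When loss biases the ratio.** The true ratio is 0.85/0.90 = 0.944.
- Equal loss of 10% in every cell: (0.9 × 0.85)/(0.9 × 0.90) = 0.944, unchanged.
- 30% of mpMRI-only detections lost, 10% elsewhere: (0.6975 + 0.0675)/(0.6975 + 0.0875) = 0.975.
- 30% of micro-US-only detections lost, 10% elsewhere: (0.6975 + 0.0525)/(0.6975 + 0.1125) = 0.926.

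At a true ratio of 0.76 (assumed discordance 0.30), simulated false non-inferiority is about 7% with no loss or with equal 10% loss. It is about 24% when mpMRI-only detections are lost at 30% against 10% elsewhere. With the imbalance reversed (mpMRI-only detections all kept, 20% of the rest lost) it is about 1%. These loss patterns are illustrations, not predictions.

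**The case against.** The strongest reply is that incomplete need not mean any single missing item. Section 5.9.8 speaks of completed subjects, which allows a reading based on finishing the procedure, and some items are optional (prostate volume, 5.4.6) or collected when available (whole-mount pathology, 5.7.1). This stands in part: the literal reading is not the only one. But the text does not choose between readings, and that is itself the defect.

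Monitoring also helps. Section 5.8.5 has the monitor verify that CRFs are complete, 5.8.5.1 requires follow-up of missing data, and saved sweeps and images might allow a missed score to be recovered. This too stands in part, because no rule covers items that cannot be recovered.

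The loss rates are assumed. Items from one session probably go missing together, which at the same item rate drops fewer men than independence implies. Nor is 24 a firm floor: 5.8.6 speaks of 12 systematic samples, 5.4.6 of filling in up to 12. All of this stands.

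A reader might infer three stronger points that the documents do not support:
- *The trial becomes underpowered.* On the plan's inputs, power by formula stays above 80% even with half the csPCa men lost.
- *Losing csPCa men more often biases the result.* Sensitivity is conditional on csPCa, so such loss does not by itself move a paired ratio. Bias needs loss that differs by which modality detected the cancer.
- *An unfinished mpMRI part wrongly deletes the micro-US result.* Operator 2 goes last (5.4.6), but if mpMRI sampling never took place there is no pair to analyse.

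**Conclusion.** The concern holds as a defect in the rule. Sections 5.9.9 and 5.9.10 exclude whole subjects on an undefined criterion not tied to the endpoint, they can discard men whose primary result is known, and they conflict with 5.8.1.6. The plan should be changed; the point does not undermine the design.

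The number affected cannot be derived from the documents. Under the independence assumption with 24 items, 0.5% to 1% missing per item removes 11% to 21% of men and leaves about 64 to 57 of 72 csPCa men, with power at about 96% to 94%. The greater risk is selection: a ratio shifted in either direction, and a false non-inferiority rate that could rise severalfold, but only if loss depends on which modality found the cancer. The documents neither show that it would nor prevent it. The 'As Intended' repeat in 5.9.8 only narrows the set further, and no missing-data sensitivity analysis is planned.

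**What to change.** Replace the incomplete-data clause in 5.9.9 with an endpoint-specific rule and align 5.9.10:
- A man enters the primary analysis when pathology is available for the systematic cores and for the targeted cores of both modalities. A man with no target in a modality counts as having no targeted detection there.
- Missing PRI-MUS scores, images, volume or lesion measurements remove him only from analyses that use them.
- Exclusions are reported by reason and modality.
- Men with unfinished targeted sampling in one modality are presented both included and excluded. Scoring them on the cores obtained should not be the sole primary rule: mpMRI sampling comes second, and truncating it can only lower mpMRI detection, which favours micro-US.

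Reconcile 5.8.1.6, 5.9.8, 5.9.9 and 5.9.10 so that they describe one primary population, with completed defined, before results are examined. The cost is a few sentences and denominators that differ between endpoints, which one table can show. No new data or subjects are needed.

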#### **5.9.10 Treatment of missing, unused data**

If a study subject withdraws from the main trial prior to having his biopsy, his consent form will be retained, and the reason for exclusion of the data will be handwritten on the form as "withdrawn prior to biopsy". Similarly, if a study subject withdraws from the main trial following his biopsy, his consent form and CRF will be retained, and both will be marked "withdrawn following biopsy".

This will allow data to be collected about the number of patients that withdrew from the investigation prior to the biopsy procedure, and the number that withdrew after the procedure.

The same process will be applied to any circumstance of incomplete or incorrect data, with an indicator handwritten on his consent form and CRF to provide information about why the record is not used for analysis.

#### **5.9.11 Exclusion of data**

Conditions that would result in the exclusion of data would be if any data verification activity showed that data was recorded on the CRF incorrectly, or if the pathology report showed any inconsistency with information on the CRF.

If such incorrect data was discovered, data for this subject will not be included in any analysis, and the CRF for the subject will be marked to indicate that the data is excluded.

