### **5.9.2 Sample size**

The trial will include 120 subjects. It is not anticipated that additional subjects will be required, however if a subject drops out before the biopsy procedure they may be replaced as described in section 5.8.1.6.

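### Section 5.9.11 drops a subject from every analysis for any CRF error, with no rule to correct the entry from source and keep the subject, and its precedence over 5.8.1.6 and 5.9.8 is not stated

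*Combined protocol and SAP*

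**What the plan says.** Section 5.9.11 has two triggers. One applies "if any data verification activity showed that data was recorded on the CRF incorrectly"; the other is any inconsistency between the pathology report and the CRF. The consequence is the same for both: "If such incorrect data was discovered, data for this subject will not be included in any analysis". The last paragraph of 5.9.10 extends the handling of withdrawn subjects to data errors: "The same process will be applied to any circumstance of incomplete or incorrect data", with the record marked to show why it is not used. Section 5.9.9 also leaves out subjects who withdraw "or for whom the collected study data is incomplete".

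Two other sections define the analysis population more widely. Section 5.8.1.6: "Case data for all enrolled study subjects will be included in the analyses". Section 5.9.8: "All analyses will be conducted on all enrolled and completed subjects", with a repeat on the as-intended population, "which includes only subjects for which there were no major protocol deviations". Neither mentions removal for CRF error.

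On data checking, 5.8.5 has the monitor verify that CRFs agree with source. Section 5.8.5.1 plans verification of all data and follow-up of inconsistencies. Section 5.8.6 attaches the pathology and mpMRI reports to the CRF, has the Principal Investigator check both entries, and stores an image for every sample. Sections 5.8.6 and 5.10.2 have sponsor personnel compare CRFs, pathology reports and images, partly while the analysis is under way. Section 5.10 has them transfer the data to the analysis tool, and 5.9.1 gives the analysis to an independent biostatistician.

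**The concern.** A clerical error is normally a reason to issue a query, not to discard the subject. Take a Gleason grade copied wrongly from the pathology report to the CRF. The attached report shows the correct grade, so the csPCa result is known, yet 5.9.11 removes the subject from the primary comparison and from everything else.

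Three things are at stake. Valid paired results are lost although they could be recovered at little cost. The primary analysis set comes to depend on data-entry accuracy. And because the precedence of 5.9.9 to 5.9.11 over 5.8.1.6 and 5.9.8 is not stated, two analysts could each follow the plan and analyse different sets.

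There is also a possible route to selection. The checks are made by sponsor personnel with pathology in hand, and no blinding is described. One example check in 5.8.6 is set off by a result pattern (targeted samples negative, systematic samples positive). Extra scrutiny of such subjects, combined with removal for any error found, could tie exclusion to outcome.

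**Working it through.** **1. Is there a correct-and-retain rule?**

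- 5.8.5 and 5.8.5.1: consistency with source is verified, and inconsistent data are followed up. What follows for the entry or the subject is not stated.
- 5.8.6: accuracy checks and follow-up of unusual data. Correction is not stated.
- 5.9.7: the analysis algorithm may be modified for unexpected data; the data are not.
- 5.9.10 and 5.9.11: these do state what happens to incorrect data, namely that the record is not used.
- 5.10.2: CRFs, pathology reports and images are compared. The consequence is not stated.

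So the only stated consequence of an error is removal.

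**2. How many subjects would be lost?** The documents give no error rate. As an assumption only, take 12 to 16 independent entries per subject (12 systematic PRI-MUS scores, plus a few others). The share of subjects with at least one error is 1 − (1 − e)^k:

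| Assumed error per entry, e | k = 12 | k = 16 |
|---|---|---|
| 0.5% | 5.8% | 7.7% |
| 1% | 11.4% | 14.9% |
| 2% | 21.5% | 27.6% |

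**3. The plan's own power figure.** Inputs: prevalence 60% (5.9.1); sensitivities 0.85 and 0.90, and 80% agreement (5.9.3); margin 0.76 with a one-sided 95% bound (5.9.5). I read 80% agreement as 20% discordant among csPCa cases. The plan names McNemar's test but gives no interval formula, so I used the paired log ratio, SE = √((b + c)/(A·B)), where b and c are the discordant counts and A and B the positives per modality.

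- Cases: 120 × 0.60 = 72.
- ln(0.85/0.90) − ln(0.76) = 0.2173.
- SE = √(0.20/(0.85 × 0.90 × 72)) = 0.0603.
- Power by formula = Φ(0.2173/0.0603 − 1.645) = 97.5%.
- Cases needed for 80% power: (1.645 + 0.842)² × 0.20/(0.85 × 0.90)/0.2173² = 34.2, and 34.2/0.60 gives 58 subjects.

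The stated 80% at 120 is therefore not reproduced. The exact procedure used for the plan's calculation is not given, so both starting points are carried forward.

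**4. Power with random exclusion.** Column A is simulated (200,000 trials per N, binomial number of cases, cell probabilities 0.775/0.125/0.075/0.025). Column B takes 80% at 120 as given and scales: Φ(√(1 − d) × (1.645 + 0.842) − 1.645), with d the share excluded.

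| Excluded | N left | A: plan's inputs | B: 80% at 120 as given |
|---|---|---|---|
| 0 | 120 | 95.5% | 80% |
| 10% | 108 | 93.8% | 76% |
| 20% | 96 | 91.4% | 72% |
| 30% | 84 | 88.6% | 67% |
| 50% | 60 | 78.8% | – |

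**5. How far can one exclusion move the estimate?** Expected table for 72 cases: discordant 0.20 × 72 = 14.4; difference 0.05 × 72 = 3.6; hence mpMRI-only 9.0, micro-ultrasound-only 5.4, both 61.2 − 5.4 = 55.8, neither 1.8. Ratio 61.2/64.8 = 0.944. After removal of one case:

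- mpMRI-only: 61.2/63.8 = 0.959
- micro-ultrasound-only: 60.2/64.8 = 0.929
- positive on both: 60.2/63.8 = 0.944
- missed by both: unchanged

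The estimate can move either way, and every value stays well above 0.76.

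**The case against.** The best defence is that a section on exclusion of data is naturally read as qualifying the general statements in 5.8.1.6 and 5.9.8, and that monitoring, Principal Investigator checks and follow-up would resolve most errors at the site, leaving 5.9.11 for the remainder. The first part stands to this extent: a reader might infer a flat contradiction, but the documents support only unstated precedence. The second part is inference. Section 5.9.11 is set off by any verification activity, and no section says that a resolved error keeps the subject in.

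Stronger readings also go too far:

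- **Biased exclusion.** A reader might infer that the sponsor would remove unfavourable subjects. A rule without a threshold, applied with full verification, leaves little discretion, and the analysis itself is independent. It is a risk and not a stated outcome.
- **An underpowered trial.** This depends on an unknown error rate and on which starting power is believed.
- **Inverted severity.** A subject with a major protocol deviation stays in the main analysis, while one with a CRF error leaves both analyses. But adherence and data reliability are different grounds for exclusion, so this is not decisive.
- **No replacement.** Section 5.9.2 says "if a subject drops out before the biopsy procedure they may be replaced as described in section 5.8.1.6", but 5.8.1.6 itself sets no pre-biopsy limit. Replacement after exclusion is unclear rather than ruled out.
- **PRI-MUS errors are always irrelevant.** They are not: a score of 3 or more marks a region as suspicious before micro-ultrasound targeting (5.4.6), so a wrong score may cast doubt on whether a sample was targeted or systematic.

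**Conclusion.** The point holds, and the plan should be changed. As written, a stated rule discards valid paired csPCa results for errors that attached or stored sources could settle, and it leaves the primary analysis set open to two readings. Confidence is high in the textual gap and low in the amount of harm.

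The loss cannot be sized from the documents. With 20% of subjects excluded at random, power is about 91% on the plan's inputs with my choice of interval, or about 72% from the plan's stated 80%. Both rest on an assumed exclusion rate, on exclusion unrelated to result, and on no replacement. Outcome-related exclusion remains possible, with unknown size and direction.

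**What to change.** Replace 5.9.11 and the last paragraph of 5.9.10 with the following.

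1. Every discrepancy is queried, the CRF is corrected from source with an audit trail, and the subject is retained. Transcription errors are corrected to the pathology or mpMRI report. PRI-MUS, location and sample-type entries are corrected only from records made at the procedure (stored image, jar label), by someone without sight of that subject's pathology. The PRI-MUS score is not re-read.
2. An unresolved entry that determines neither the csPCa result nor the modality of the sample is set to missing, only for the analyses that use it.
3. A biopsied subject is excluded from the primary analysis only if the pathology result or the modality of the sample cannot be established. This is decided before the analysis data are finalised and without sight of results by modality.

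State that 5.8.1.6, 5.9.8 and 5.9.9 are subject to this rule. Report exclusions by reason. Add a sensitivity analysis, limited to biopsied subjects excluded under (3), that sets the unestablished result to detected and then to not detected for each modality.

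Cost: wording changes, a query log, and a blinded step for PRI-MUS, location and sample-type corrections. Full verification and image storage are already planned. The documents do not give the staff time that queries would need. Design and sample size do not change.
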